All participants will undergo the ***Hypnotic Stroop Scan Session Day***. All participants will receive the identical pre-rTMS scan session. One-half (n=50) will receive active rTMS and one-half (n=50) will receive sham rTMS (two arm, double-blind, sham-controlled). All participants will receive the identical post-rTMS scan session. Changes in resting state *functional connectivity* between L-DLPFC and dACC in the active rTMS versus the sham rTMS conditions will be assessed. This primary endpoint is a between-group comparison. We will also measure the difference in brain *activation* during the hypnotic induction, and Stroop task (after post-hypnotic suggestion) between the active and sham rTMS. This will also be a between-groups comparison. Using the *Hypnotic Induction Profile (HIP)* and *Hypnotic Intensity Scale (HIS)*, we will compare the change in hypnotizability and hypnotic intensity score between the active and sham rTMS groups.

All participants will undergo the ***Hypnotic Analgesia Scan Session Day***. All participants will complete identical pre- and post- rTMS scan session. One-half will receive active rTMS and one-half will receive sham rTMS. Changes in resting state *functional connectivity* between L-DLPFC and dACC in the active rTMS versus the sham rTMS conditions will be assessed. This primary endpoint is a between-group comparison. This scan-session also addresses a secondary aim of determining the difference in functional connectivity within the hypnotic analgesia network between the active and the sham rTMS groups. This will be a between-groups comparison. We will also compare the activation within the hypnotic analgesia network between the active and sham rTMS groups. This will be a between-groups comparison. We will also utilize a perturbation technique to probe the hypnotic induction in an alternative way. Finally, we will compare the difference in pain thresholds between the active and sham rTMS groups.

Interventions and Duration

Intervention: We will compare active versus sham rTMS as a technique for modulating the neural

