- Spectroscopy: Non-invasive magnetic resonance spectroscopy (MRS) will be used to quantitatively measure brain metabolites, including both inhibitory and excitatory neurotransmitters as well as markers of inflammation.

Pre-rTMS Stroop Assessment

Hypnotic Stroop and Non-Hypnotic Stroop Pre-rTMS Scan Session: This session includes all of the pre-rTMS questionnaires, behavioral evaluations and scans necessary to compare to the post-rTMS.

- Medication Washout, Drug Screen, Pregnancy Test Form: This form will be administered at the beginning of each pre-rTMS assessment to ensure medication washout compliancy (if applicable), document drug screen results, and screen for pregnancy (if applicable).
- Hypnotic Induction Profile: This administration of the HIP will serve as the baseline measure for comparison after the rTMS stimulation session(87). HIP will be measured on three separate occasions throughout the stroop assessment visit - 1) immediately following the pre-rTMS stroop MRI session, 2) immediately following rTMS, and, 3) immediately following the post-rTMS stroop MRI session.
- Stroop Task: This administration of the Stroop task will serve as the baseline measure for comparison to the post-rTMS session(32, 118).
- Pre-TMS Hypnotizability Scan Session (1 hour duration)
 - Structural Acquisition (T1): This structural scan is necessary for several reasons: demonstration that the participant's brain is structurally normal, imaging analysis, and rTMS targeting(81).
 - BOLD fMRI Acquisitions
 - Resting State: This is the baseline scan required for the primary endpoint. Individuals with high hypnotizability have been demonstrated to have higher functional connectivity between the dorsolateral prefrontal cortex and the dorsal anterior cingulate cortex (31).
 - Stroop Task: Brain activity while performing conflict tasks has been demonstrated to be different depending on a subject's level of hypnotizability. This baseline would demonstrate the subject's normal functional brain response to the Stroop Task

(32). Functional brain response to the stroop task will be measured following hypnosis (Hypnotic Stroop) and non-hypnosis (Non-Hypnotic Stroop) audio instructions. These acquisitions will be randomized to prevent order effects. Highly hypnotizable individuals can have a loss of the Stroop Effect with specific post-hypnotic instruction (119, 120) which correlates with the reduction in neural activity during conflict (35).

Pre-rTMS Analgesia Assessment

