Pre-rTMS Analgesia Session: This hour-long scan session includes all of the pre-rTMS questionnaires, behavioral evaluations, and scans necessary to compare to the post-rTMS.

- Medication Washout, Drug Screen, Pregnancy Test Form: This form will be administered at the beginning of each pre-rTMS assessment to ensure medication washout compliancy (if applicable), document drug screen results, and screen for pregnancy (if applicable).
- Pain Thresholds: Baseline heat-pain thresholds and supra-pain thresholds will be determined for each volunteer based on responses to computer-controlled thermal stimuli delivered to the left forearm with a 30 x 30 mm advanced thermal stimulator (ATS) thermode (Medoc Pathway Model ATS). Thresholds will be measured using a standard method of limits protocol. Specifically, thermal pain threshold and tolerance values will be assessed outside the MRI scanner to identify a moderate pain intensity value that will be applied during the hypnotic and non-hypnotic analgesia MRI scans. The moderate pain intensity value will be used for both pre- and post-rTMS analgesia MRI sessions.
- Hypnotic Induction Profile: This administration of the HIP will serve as the baseline measure for comparison after the rTMS stimulation session(87). HIP will be measured on three separate occasions throughout the stroop assessment visit - 1) immediately following the pre-rTMS analgesia MRI session, 2) immediately following rTMS, and, 3) immediately following the post-rTMS analgesia MRI session.
- Pre-TMS Scans
 - Structural Acquisition (T1): This structural scan is necessary for several reasons: demonstration that the participant's brain is structurally normal, imaging analysis, and rTMS targeting (81).
 - BOLD fMRI Acquisitions
 - Resting State: This is the baseline scan required for the primary endpoint. Individuals with higher hypnotizability have been demonstrated to have

higher functional connectivity between the dorsolateral prefrontal cortex and the dorsal anterior cingulate cortex (31).

- Pain Induction: Functional brain responses to acute, thermally, induced pain, will be measured using the moderate pain intensity value following hypnosis (Hypnotic Analgesia) and non-hypnosis (Non-Hypnotic Analgesia) audio instructions. These acquisitions will be randomized to prevent order effects. Hypnotic analgesia during pain induction has been demonstrated to be instruction specific (38, 44) and produce alterations in functional connectivity (123).

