6.2.5 Post-rTMS (Active and Sham) Evaluations

Post-rTMS Stroop Assessment

Hypnotic Stroop and Non-Hypnotic Stroop Pre-rTMS Scan Session: This session includes all of the post-rTMS behavioral evaluations and scans necessary to compare to the pre-rTMS.

- Hypnotic Induction Profile: This administration of the HIP will serve as the post-rTMS measure for comparison to the pre-rTMS stimulation session.
- Post-TMS Hypnotizability Scan Session (1 hour duration)
 - Structural Acquisition (T1): This structural scan is necessary for several reasons: demonstration that the participant's brain is structurally normal, imaging analysis, and rTMS targeting(81).
 - BOLD fMRI Acquisitions
 - Resting State: This is the scan required for evaluation of the primary endpoint. Individuals with high hypnotizability have been demonstrated to have higher functional connectivity between the dorsolateral prefrontal cortex and the dorsal anterior cingulate cortex (31).
 - Stroop Task: Brain activity while performing conflict tasks has been demonstrated to be different depending on a subject's level of hypnotizability. These scans will demonstrate the subject's functional brain response to the Stroop Task post-rTMS. Functional brain response to the stroop task will be measured following hypnosis (Hypnotic Stroop) and non-hypnosis (Non-Hypnotic Stroop) audio instructions. Randomization of hypnosis and non-hypnosis scan order for each participant will be kept consistent between both pre- and post-rTMS scans. Highly hypnotizable individuals can have a loss of the Stroop Effect with specific post-hypnoitic instruction (119, 120) which correlates with the reduction in neural activity

during conflict (35).

Post-rTMS Analgesia Assessment

Post-rTMS Analgesia Session: This hour-long scan session includes all of the post-rTMS behavioral evaluations and scans necessary to compare to the pre-rTMS.

- Hypnotic Induction Profile: This administration of the HIP will serve as the baseline measure for comparison after the rTMS stimulation session(87).
- Pre-TMS Scans
 - Structural Acquisition (T1): This structural scan is necessary for several reasons: demonstration that the participant's brain is structurally normal, imaging analysis, and rTMS targeting (81).
 - BOLD fMRI Acquisitions

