 - Resting State: This is the baseline scan required for the primary endpoint. Individuals with higher hypnotizability have been demonstrated to have higher functional connectivity between the dorsolateral prefrontal cortex and the dorsal anterior cingulate cortex (31).
 - Pain Induction: Using the same moderate thermal pain values identified above, functional brain responses to acute pain, will be measured following hypnosis (Hypnotic Analgesia) and non-hypnosis (Non-Hypnotic Analgesia) audio instructions. Randomization of hypnosis and non-hypnosis scan order for each participant will be kept consistent between both pre- and post-rTMS scans. Hypnotic analgesia during pain induction has been demonstrated to be instruction specific (38, 44) and produce alterations in functional connectivity (123).

MR Spectroscopy Assessment (Optional)

Imaging Procedure

- Structural Acquisition (T1/T2/DWI): A structural scan will be acquired for imaging analysis.
- 1H-MRS Spectroscopy: MEGA-PRESS (GABA/Glx) and NFL-PRESS (Broad spectra) spectroscopy sequences will be acquired bilaterally within the left and right DLPFC using a cutting-edge automated voxel placement procedure that precisely targets the identified connectivity coordinates.
- Resting State fMRI: A BOLD fMRI acquisition will be acquired while the participant is at rest to assess functional connectivity between the insula and DLPFC (bilaterally)

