Valchev	Motor/Somatosensory cortex	BOLD	2.86192037
Valchev	Motor/Somatosensory cortex	BOLD	1.23857467

Table 4: Effect sizes for rTMS induced changes in brain activity as a surrogate for hypnosis (Jiang 2016)(34) modulated by rTMS(159, 161-163).

As our study is a randomized controlled study, in line with the intention to treat principle, our primary analysis will be a straightforward comparison of the active versus sham groups using a linear model. Following the convention in imaging studies, we will conduct our primary analyses treating the contrast (baseline vs post) as one univariate outcome. The univariate model described below can be estimated either using linear regression or analysis of variance procedures.

A continuous outcome Y for individual i ($i=1,2,3,\dots, N$) can be expressed as $Y_i = \alpha + \gamma Z_i + \varepsilon_i$, where α is the mean of the sham group, Z_i is the randomized treatment assignment status (0=sham, 1=active), γ is the treatment effect, and $\varepsilon_i \sim N(0, \sigma^2)$. According to random assignment, the estimate of γ will be interpreted as causal effect of treatment assignment.

We do not expect much variation across our narrowly defined subjects, although some variation is still possible. As a way of sensitivity analysis, we will also analyze the data in the linear mixed effects modeling framework allowing for random intercepts, although this is not customary in imaging studies. The linear mixed effects model described below will be estimated using the maximum likelihood estimation method implemented in SPSS or in Mplus.

The outcome Y for individual i at time point t ($t = 1,2$ for pre and post) is now expressed as

$$Y_{it} = \eta_{0i} + \eta_{1i}W_t + \varepsilon_{it}, \quad (2)$$

$$\eta_{0i} = \eta_0 + \gamma_0 Z_i + \zeta_{0i} \quad (3)$$

$$\eta_{1i} = \eta_1 + \gamma_1 Z_i + \zeta_{1i} \quad (4)$$

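### The documents conflict on which scan day supplies the primary connectivity test, and the primary analysis does not name the day

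*Combined protocol and SAP*

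**What the plan says.** All references are to the combined protocol and SAP unless the separate SAP is named.

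**Both days are labelled primary.** The Précis describes the L-DLPFC to dACC comparison under the Stroop day and continues "This primary endpoint is a between-group comparison. We will also measure the difference in brain". Under the analgesia day it describes the same comparison and continues "This primary endpoint is a between-group comparison. This scan-session also addresses a secondary aim". Section 6.2.2 says of the Stroop-day pre-stimulation scan "Resting State: This is the baseline scan required for the primary endpoint. Individuals with high hypnotizability have been demonstrated", and of the analgesia-day one "Resting State: This is the baseline scan required for the primary endpoint". In section 6.2.5 the Stroop-day post-stimulation entry is "Resting State: This is the scan required for evaluation of the primary endpoint". The analgesia-day post-stimulation entry is "Resting State: This is the baseline scan required for the primary endpoint. Individuals with higher hypnotizability have been demonstrated", which calls a post-stimulation scan a baseline.

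**Section 9.6.1 points to one session.** Its subsection on scans for the primary outcome measure names only the hypnotizability session. Section 6 uses that title only within the Stroop assessments, for example "Post-TMS Hypnotizability Scan Session (1 hour duration".

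**One test is planned.** Section 9.2 says "we will conduct our primary analyses treating the contrast (baseline vs post) as one univariate outcome", and 9.7 repeats this. The model in 9.2 has one outcome per participant and no index for day. Power is computed for one comparison of 40 versus 40 at two-sided 0.05.

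**Both days together.** Sections 9.1 and 9.7 say the same sample is used twice for reasons of power. Section 9.7 models the two days as multivariate outcomes, but as a repeat of the main analyses to gauge the effect of missing sessions, described as sensitivity. The separate SAP covers HIP change and the test of the blind only.

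**The concern.** A primary test needs one outcome per participant, fixed in advance. Here two candidate values exist and the text supports more than one choice. Taking 9.6.1 as governing gives the Stroop day. Taking the Précis and section 6 at face value gives two comparisons that both carry the primary label. Taking the power rationale as a reason to pool gives an average. These choices differ in power, and the plan states no conclusion for a trial in which one day is significant and the other is not. Leaving the choice open until results are known would also weaken any claim that the reported test was the planned one.

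**Working it through.** **Inputs.** From section 9.2: two-sided alpha 0.05, 40 usable per arm, d = 0.8 for planning, and d = 0.69 from the one prior study of this connection. Assumed, because the documents give neither: the between-day correlation r of the two change scores (0, 0.5, 0.8), and the same-day pre-post correlation a (0.3, 0.5, 0.7).

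**The plan's own figure.** The noncentrality is d × √(40/2), with 78 degrees of freedom. For d = 0.8 it is 3.578 and power is 0.942; for d = 0.69 it is 3.086 and power is 0.862. Section 9.2 states 0.8 for d = 0.8, which these inputs do not reproduce. That is a separate matter, and nothing below depends on it.

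**Exactly one day significant, same true effect on both days.** At r = 0 this is 2p(1 − p):

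- d = 0.8: 2 × 0.942 × 0.058 = 10.9%
- d = 0.69: 2 × 0.862 × 0.138 = 23.8%

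For r > 0 it was simulated with two-sample t tests, 100,000 trials per setting.

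| r | d = 0.8 | d = 0.69 |
|---|---|---|
| 0 | 10.9% | 23.8% |
| 0.5 | 8.5% | 17.4% |
| 0.8 | 5.6% | 11.3% |

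**Power under each definition.** For the two-day average the standardised effect is d/√((1 + r)/2) if both days carry it, and (d/2)/√((1 + r)/2) if only one does.

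| Definition | r = 0 | r = 0.5 | r = 0.8 |
|---|---|---|---|
| One named day, d = 0.69 | 0.86 | 0.86 | 0.86 |
| Both days required, d = 0.69 | 0.74 | 0.78 | 0.81 |
| Average, effect on both days, d = 0.69 | 0.99 | 0.94 | 0.89 |
| Average, effect on one day only, d = 0.69 | 0.58 | 0.42 | 0.36 |
| Average, effect on one day only, d = 0.8 | 0.70 | 0.53 | 0.46 |

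If the one day that carries the effect is the day named, its power stays at 0.86 (d = 0.69) or 0.94 (d = 0.8).

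**Type I error if either day could count.** At r = 0 it is 1 − 0.95² = 9.75%. From the bivariate normal it is 9.07% at r = 0.5 and 7.81% at r = 0.8. The plan states no either-day rule.

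**Optional baseline adjustment.** The covariate is the resting value from the pre-rTMS scan of the first stimulation day, which precedes any cTBS. Assume unit variances, same-day correlation a, and all cross-day correlations equal (which implies r = 0).

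- *Named day.* The change has variance 2(1 − a). Its covariance with the covariate is −(1 − a) for the half of participants who have the named day first and 0 for the other half, so −(1 − a)/2 pooled. The variance factor is 1 − [(1 − a)²/4]/[2(1 − a)] = 1 − (1 − a)/8, that is 0.91, 0.94 and 0.96 for a = 0.3, 0.5 and 0.7. At d = 0.69, dividing d by the square root of the factor raises power from 0.86 to 0.89, 0.88 and 0.87.
- *Two-day average.* The variance is 1 − a and the covariance −(1 − a)/2, so the factor is (3 + a)/4, that is 0.83, 0.88 and 0.93.

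**The case against.** The strongest reply is that 9.6.1 defines the primary outcome and does name a session. Only the Stroop day has a hypnotizability session, and only that day's post-stimulation scan is described as the one needed to evaluate the primary endpoint. The analgesia-day post-stimulation entry looks like text carried over from the pre-stimulation list. This stands as far as it goes: the Stroop day is the best-supported reading, and the last of those labels is weak evidence for the analgesia day. It does not remove the conflict. The Précis and the analgesia-day pre-stimulation entry still give that day the same status, 9.2 and 9.7 name no day, and nothing says which text prevails.

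Second, 9.7 does contain a joint model of the two days, with scan order included. That is correct, so it would be wrong to say that no combination rule exists. It is not a rule for the primary test.

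Third, a reader might infer from the power rationale in 9.1 that the days were meant to be pooled. The sentence before it assigns the days to different aims, so it can equally mean that each aim gets the full sample. The documents do not settle this.

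Fourth, a reader might infer that the trial has two primary tests at 0.05 each and hence an inflated error rate. Sections 9.2 and 9.7 plan one univariate test, and no text lets either day count as success.

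Finally, stimulation follows the same protocol on both days (section 6.2.4), so an effect confined to one day is a what-if, not something the documents predict.

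**Conclusion.** The conflict is real and should be fixed. It concerns which contrast is primary; the change-score method itself is valid. The measurable consequence is a 6–11% chance (d = 0.8) or 11–24% chance (d = 0.69) of a split result for which the plan states no conclusion. This assumes equal true effects on both days, 40 per arm and a between-day correlation from 0.8 to 0. An error rate of about 8–10% would arise only under an either-day rule that the plan does not state, so it measures the risk of leaving the choice open and is not a property of the plan. Baseline adjustment is an improvement available from data already collected, not the correction of an error, and for a named day its gain is small.

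**What to change.** 1. In 9.2, 9.6.1 and 9.7, state one primary test at two-sided 0.05. The reading closest to 9.6.1 is the arm difference in the Stroop-day pre-to-post change, with the analgesia-day change reported as supportive. In that case, correct the primary-endpoint labels on the analgesia day in the Précis, 6.2.2 and 6.2.5.
2. If the sponsor intended both days, define the outcome as the average of the two same-day changes. Use the likelihood model already planned in 9.7 for participants with one usable day, and note the loss of power if only one day carries an effect.
3. Under either choice, report both days' estimates and correct the baseline label on the analgesia-day post-stimulation scan. The separate SAP describes data already collected, so date the clarification and state its timing relative to unblinding.
4. Optionally, adjust the primary test for scan order and for the resting value from the pre-rTMS scan of the first stimulation day, and keep the unadjusted change as sensitivity. Identify that scan explicitly, since the earlier targeting visit also includes a resting scan. Do not constrain the arms to be equal at the second stimulation day's pre-scan: section 3 keeps each participant in the same arm on both days, so that scan follows stimulation.

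The cost is wording, label corrections and, if item 4 is taken up, two model terms. No new data or visits are needed. Naming one day gives up the precision from the other; averaging gives up power if the effect is confined to one day.

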9.3 Stimulation Group Assignment Procedures

Stimulation Group Assignment Procedures: Random assignment is a procedure used in experiments to create study groups with similar characteristics so that the groups are equivalent at the beginning of the study. We perform randomization using permuted block to ensure balancing between arms.

Randomization Rationale and Procedure: The *MagLink* software program is used by the principal investigator to define the stimulation protocol for each patient enrolled in the study. This includes defining whether a given patient is to receive real or sham stimulation. When the protocol has been defined it is downloaded to a Patient Key (USB memory device).

Maintenance of Randomization Codes: In order to use Active/Placebo (A/P) for different groups, an Excel spreadsheet with number series for operators and subjects (active stimulation as well as placebo stimulation) is stored by a separate clinical research coordinator who is trained to maintain the blind. Subjects codes (Randomization Stimulation Numbers) are followed by 0 or 1, where “0” is placebo stimulation and “1” is real stimulation.

Maintaining Appropriate Masking: All site personnel will be masked to the stimulation group assignment (active versus sham) for each subject. Specific aspects of the trial design are intended to optimize the integrity of the masking and all staff will be trained to the procedures for masking during the site initiation visit. In addition to those procedures, the treater will be provided with individually sealed and numbered envelopes, corresponding to subject randomization numbers.

Procedures for Planned and Unplanned Breaking of Randomization Codes: In the case of an emergency, an envelope may be opened to identify the TMS stimulation group assignment for a particular subject. In all circumstances, the Principal Investigator (PI) will notify NCCIH prior to unmasking the TMS stimulation group assignment for any subject, if possible. In the event that the emergency circumstances preclude first notifying NCCIH immediately, the PI will contact NCCIH within one business day and provide the reason(s) for unmasking and date of opening of the envelope must be documented in the subject’s files. The unmasking must also be documented on the Adverse Event page of the CRF, and in the subject’s source documents. Additionally, the PI will submit a written explanation describing the unmasking within 5 working days to NCCIH.

Blinding and Unblinding methods: For stimulation sessions, *MagLink* will require use of the Cool-B65 A/P coil that has a built-in position sensor used to ensure that the correct (active or sham) side of the coil faces towards the patient's head. If the coil position is wrong the operator will get a "Flip Coil" prompt on the MagPro screen. To ensure best possible blinding of patients the current stimulation provided with the Cool-B65 A/P coil should be used to stimulate the patient's skin. When a stimulation session is completed, the session data are stored on both the

Patient Key and the Operator Key. [name] and [name] are authorized to break the blind.

Circumstances for Breaking the Blind: In the event of a serious adverse device effect, the Principal Investigator will carefully assess whether breaking the blind will critically affect how a subject is treated in response to the adverse effect and whether this knowledge outweighs the implications to the scientific soundness of the study. In the case of most serious adverse effects, the study would be discontinued and symptoms treated symptomatically irrespective of the knowledge of whether the stimulation received was active or sham in nature. In these instances, having this information would not significantly alter the treatment of the adverse effect(s). As an additional safeguard against bias, the IMC has been charged with making the final recommendations for breaking the study blind. If the IMC recommends unmasking the study, the key to active or sham stimulation will be obtained from the unblinded CRC. Notation regarding the nature of the type of stimulation that the subject had been receiving will be documented in the subject's source document. If the decision to break the blind is made immediately upon learning of the adverse event, this information will be reported to the NCCIH and reviewing IRB at the time of initial adverse event reporting. If the unblinding occurs after the initial reporting, the NCCIH will be notified of the action within ten working days from the time of breaking the blind. The reviewing IRB will be notified according to their reporting guidelines if the decision is made to break the study blind after the initial reporting.

Procedure for Breaking the Blind at Study Completion: To minimize any source of bias, unblinding of the study will not be done until all subjects have completed all study phases. However, unblinding will occur if the Independent Monitoring Committee, consistent with their assigned charter and associated stopping rules, determines that it necessary to do so. At the end of the study Patient Keys are returned to the principal investigator for data analysis. The MagPro double-blinded research system ensures efficacy, accuracy and consistency. The system comes with a *MagLink* software program specifically developed for data collection in double-blinded studies. The program is used to define the stimulation protocol for each patient (real or sham stimulation).

